As the Principal Investigator, I will assure that no deviation from, or changes to the protocol will take place without prior agreement from the sponsor and documented approval from the Institutional Review Board (IRB), or other approved Ethics Committee, except where necessary to eliminate an immediate hazard(s) to the trial participants.

All key personnel (all individuals responsible for the design and conduct of this trial) have completed Human Participants Protection Training and Good Clinical Practice Training. Further, I agree to ensure that all staff members involved in the conduct of this study are informed about their obligations in meeting the above commitments.

Investigator's Signature _____ Date: ____ / ____ / ____

Investigator's Name: _____

Site Name: University of Virginia

LIST OF ABBREVIATIONS

Abbreviation	Definition
ADA	American Diabetes Association
AE	Adverse Event
AID	Automated insulin delivery
AIDANET	Automated insulin delivery as Adaptive Network
AP	Artificial pancreas
AUC	Area Under the Curve
AYA	Adolescent and Young Adult
BDC	Barbara Davis Center
BG	Blood Glucose (as assessed by a blood glucose meter)
BGM	Blood glucose meter
BPS	Bolus Priming System
CGM	Continuous glucose monitor
CSII	Continuous subcutaneous insulin infusion
DiAs	Diabetes Assistant
DKA	Diabetic Ketoacidosis
DWM	DiAs Web Monitoring
FCL	Fully automated closed-loop
HbA1c	Hemoglobin A1c
HCL	Hybrid closed loop
NAP	Neural-network artificial pancreas
RL	Reinforcement Learning
SAE	Severe Adverse Event
SG	Sensor Glucose (as assessed by a continuous glucose monitor)
SH	Severe Hypoglycemia
T1D	Type 1 diabetes
TAR	Time above range
TBR	Time below range
TIR	Time in range 70-180 mg/dL

PROTOCOL SUMMARY

Participant Area	Description
Title	Safety and Feasibility of a Machine-Learning Bolus Priming Added to Existing Control Algorithm (AIDANET)
Investigational Device	Reinforcement Learning trained Bolus Priming System (BPS_RL) added to the AIDANET algorithm and running on DiAs phone wirelessly connected to Tandem t:AP insulin pump and Dexcom CGM
Objectives	The primary objective of the project is to demonstrate feasibility and safety of the BPS_RL added to the existing AIDANET AID algorithm, used in FCL mode by adults with T1D.
Study Design	A randomized cross-over trial assessing glycemic control on AIDANET+ BPS_RL, compared to the original AIDANET algorithm, which includes two sessions studied in a supervised hotel setting: 1) using AIDANET+ BPS_RL, and 2) using the original AIDANET without modifications including the previous BPS (see IDE G240236).
Number of Sites	1
Endpoint	The primary outcome will be time in range 70-180 mg/dL for an 18-hour period, 6 PM to 12 PM on the next day, including dinner and breakfast meals.
Population	Key Inclusion Criteria: 
 • Age ≥ 18 years of age • Clinical diagnosis, based on investigator assessment, of Type 1 Diabetes for at least 1 year • Currently using insulin for at least six months. • Having used an AID system equipped with Dexcom G6 or G7 sensor within the last 3 months
Sample Size	Complete 16 participants
Treatment Groups	Randomized crossover: Participants will be randomized to two groups differing by the order of controller use: Group A: AIDANET first followed by AIDANET+ BPS_RL; Group B: AIDANET+ BPS_RL followed by AIDANET.
Participant Duration	Approximately 3 weeks, including: 1 week of remotely monitored AIDANET at home for all participants, 3 days/2 nights AIDANET vs. AIDANET+ BPS_RL crossover at a hotel, and 1 week at home remote monitored AIDANET+ BPS_RL for all participants (Figure 1).
Protocol Overview/Synopsis	Following enrollment, 1 week of AIDANET data will be collected and will be used to establish a baseline and initialize the control algorithm. Participants will be then studied at a hotel for approximately 40 hours, including two 18-hour experiments, randomly receiving either AIDANET or AIDANET+ BPS_RL. Participants will then receive the opposite intervention sequentially during the same hotel session and will then transition to 1-week remote monitored home use of AIDANET+ BPS_RL (Figure 1).

TABLE 1. SCHEDULE OF STUDY VISITS AND PROCEDURES

	Screening	AIDANET Training	AIDANET At-Home	Pre-Hotel Check-in Visit	Hotel Session 1	Hotel Session 2	AIDANET+ BPS_RL At-Home	Post-Study Check-in Visit
Location	Clinic/ Remote	Clinic	Home	Remote	Hotel	Hotel	Home	Remote
Visit	1	2	3	4	5	6	7	8
Day	1	2	3-10	10	11-13		14-21	22
Informed Consent	X							
Eligibility Assessment	X							
Medical History	X							
HbA1c		X						
Pregnancy test (if applicable)	X							
Physical Exam	X							
Vital Signs (height/weight)	X				X			
Demographic Survey	X							
INSPIRE & Technology Expectation/ Assessment Survey	X						X (post)	
Randomization	X							
AIDANET use with Remote monitoring		X	X					
AIDANET or AIDANET+ BPS_RL use					X	X		
AIDANET+ BPS_RL 1-week use with Remote monitoring							X	
Check-in visit			X				X	
Review diabetes management and AEs			X	X			X	

Contact type is Clinic Visit and Remote which includes videoconferencing, phone, text messages and emails.

TABLE 2. METRIC CAPTURE TIMELINE

	Enrollment	AIDANET At-Home	Hotel Sessions	AIDANET+ BPS_RL At-Home
Visit	1	3	5 & 6	7
Demographic Data	x			
HbA1c	x			
CGM Data		x	x	x
TIR 70-180 mg/dL		x	x	x
CGM%<54 mg/dL		x	x	x
CGM%<70 mg/dL		x	x	x
CGM%>180 mg/dL		x	x	x
CGM%>250 mg/dL		x	x	x
Mean CGM		x	x	x
Time in Automation		x	x	x
Total Daily Insulin Dose		x	x	x
Number of Boluses per Day		x	x	x
Exercise: CGM %<70 mg/dL		x	x	x
Unannounced Meals: % CGM>250 mg/dL		x	x	x

1	Table of Contents	
2	Chapter 1: Background and Introduction.....	13
3	Chapter 2: Study Synopsis	16
4	2.1 Study Objective.....	16
5	2.2 Specific Aims and Hypotheses	16
6	2.3 Study Design.....	16
7	2.4 Study Hardware/Software.....	17
8	2.5 Timing of Device Use.....	17
9	2.6 Meal Testing	18
10	2.7 Study Devices Download.....	18
11	2.8 Study System Issues.....	18
12	Chapter 3: Study Screening	19
13	3.1 Clinical Site.....	19
14	3.2 Participant Recruitment and Enrollment.....	19
15	3.3 Informed Consent and Authorization Procedures.....	19
16	3.4 Participant Inclusion Criteria	19
17	3.5 Participant Exclusion Criteria	20
18	3.6 Screening Procedures.....	21
19	3.7 Screen Failures / Participant Dropout	22
20	3.8 Personal Equipment Downloads	22
21	3.9 Surveys.....	22
22	3.10 Other Considerations	22
23	3.11 Randomization	23
24	Chapter 4: Study Devices & Training Visit	24
25	4.1 Insulin Pump and DiAs.....	25
26	4.2 Continuous Glucose Monitor.....	25
27	4.3 Blood Glucose Meter and Strips.....	26
28	4.4 Ketone Meter and Strips	27
29	4.5 Study Devices Accountability Procedures.....	27

30	Chapter 5: AIDANET At-Home Period	28
31	5.1 AIDANET use at home.....	28
32	5.2 Pre-Hotel Check-In Visit	28
33	Chapter 6: Supervised Hotel Fully Closed-Loop Period	29
34	6.1 Hotel Session	29
35	6.2 Qualifications and Role of the Staff.....	29
36	6.3 Hotel Session Check-In.....	29
37	6.4 Study Meals	30
38	6.5 Hotel Session Activities.....	30
39	6.6 Glycemic Treatment Guidelines	30
40	6.7 Hotel Session Discharge	31
41	6.8 Other Issues.....	31
42	Chapter 7: AIDANET+BPS_RL At-Home Period	32
43	7.1 AIDANET+BPS_RL use at home	32

Automated Insulin Delivery (AID) has firmly transitioned to the clinical practice of Type 1 Diabetes (T1D) and has made its first strides into insulin-using type 2 diabetes as well. High-ranking general medicine journals are now regularly publishing AID clinical trials.¹⁻⁶ Real-life data for thousands of AID users have been published, consistently showing the superiority of AID over standard therapies.⁷⁻¹³ Consensus recommendations for the use of automated insulin delivery technologies in clinical practice were published by Endocrine Reviews,¹⁴ to serve as a comprehensive guide for clinicians interested in utilizing the advantages of AID therapy.

The “brain” of any insulin delivery system is a control algorithm, which digests information from peripheral devices, e.g., a continuous glucose monitor (CGM) and insulin pump, and then directs the pump to deliver amounts of insulin that are considered optimal. Typically, this happens at a pace of every few minutes;¹⁵ thus an AID control algorithm has to be fast, efficient, and with low computational demands, particularly because the data processing is done by a device with low computing power, such as an insulin pump or a smart watch. The early studies of Hovorka^{16,17} and Steil¹⁸ outlined two major types of algorithms now in use – model-predictive control (MPC)¹⁷ and proportional-integral-derivative (PID).¹⁸ A modular controller based on the user’s state estimation was introduced in 2009,¹⁹ which later became the algorithm behind Tandem’s Control-IQ AID system.^{1,2,4,7} In 2010, two new algorithms were introduced: Zone MPC²⁰ – a strategy to minimize hyper- and hypoglycemic events, and MD Logic using clinical knowledge and fuzzy logic models to drive insulin delivery.²¹ In combination with PID, MD Logic powered the MiniMED Advanced Hybrid Closed-Loop (AHCL) system.^{22,23} A MPC-PID mix was introduced to drive dual-hormone AP²⁴, and is now used in studies with the dual-chamber iLet pump.²⁵ Overall, a PubMed search on artificial pancreas, or AID, or closed loop algorithms, identified 555 papers proposing AID controllers. To date, at least 6 of them have been implemented in devices used in clinical practice.

However, virtually all contemporary AID algorithms rely on approximations of the human metabolic system by equations (in the case of PID) or by a model, in the case of MPC.¹⁵ Empirical controllers have been introduced as well, incorporating clinical knowledge in the insulin dosing decision making process.²¹ Adaptive AID algorithms have been introduced over the years, attempting to compensate for the ever-changing physiology of their users.²⁶⁻²⁹ This is typically done by using a person’s data from the previous hours/days/weeks and re-estimating accordingly the parameters of the model underlying the control algorithm. Mathematically, such re-estimation requires rather complex numerical methods, as closed-form solutions rarely exist. As a result, contemporary adaptive algorithms cannot run on devices with low processing power, such as insulin pumps. In some cases, such as the CamAPS AID system, the demand for computing power is satisfied by placing the control algorithm on a smart phone.³⁰ But, integrated AID devices that do not rely on external computing resources, e.g. AHCL,^{22,23} \Control-IQ^{1,2,4,7} and \Omnipod 5,³¹ cannot afford running complex nonlinear algorithms.

To summarize, the current AID systems face two major shortcomings: (1) Any learning or adaptation of the AID algorithm is based only on the data patterns of this algorithm’s user and does not have a mechanism to utilize the vast amounts of data collected in various databases, and (2) Any learning or adaptation of the AID algorithm requires substantial computing power.

Contemporary Data Science methods, such as machine learning and AI, can remedy both of these shortcomings. The first step towards that end was translating an established AID control algorithm, into a Data Science “environment,” e.g., creating a neural network approximation of a model-predictive controller. In early 2024, we conducted a pilot-feasibility study of a conceptually new AID algorithm – a Neural-network artificial pancreas (NAP) that was a result from a process of encoding an insulin dosing rule into a neural network – clinicaltrials.gov ID NCT05876273, IDE #G230052.³² This process was based on the concept of a “Saturated Dataset”, e.g., an ensemble of examples of the dosing rule computation that is sufficiently dense and sufficiently wide, so that the deviation between the original dosing rule and the resulting neural network is kept within predefined limits.³³ If the preset limits are sufficiently small, the neural net can be considered a safe and efficacious alternative to the original dosing rule. The results from this first randomized crossover study showed that the NAP concept works as intended – all predefined conditions for success, i.e., proximity of NAP to its original UMPC algorithm, were met.³² Moreover, any glycemic control discrepancies between the NAP and UMPC sessions of the study could be entirely attributed to external factors – the behavioral and physiological variance of the study participants between the two sessions. When a clean experiment was made and NAP and UMPC were presented with identical input data as done throughout the duration of this study, the insulin dosing recommendations of the two algorithms were virtually identical. Further, the computational demands of NAP were 6-fold lower compared to the UMPC, without requiring third-party numerical solvers or libraries. While here this comparison was done on a computer (intelCore i5) and both 1.4 ms and 8.3 ms are exceedingly small, this difference would be of essence when the algorithm is scaled down to fit in an insulin pump. Thus, this pilot-feasibility study tested the concept of a neural-network encoding of a complex model-predictive AID control algorithm. In a randomized crossover trial, the neural net demonstrated similar performance to the original algorithm, at a fraction of the computational demands.³²

The second step was a further optimization of the neural network structure and size. This was completed in the summer of 2024 and IDE #G240236 was submitted to the FDA, with the objective to conduct a trial validating the optimized AIDANET (Automated insulin delivery as Adaptive Network) system during a 2-night house/hotel session and during 1 week at home. This IDE was approved on 10 Oct 2024 and the AIDANET trial is anticipated to be completed by the end of 2024 (NCT06633965). Participants use the AIDANET system in fully automated closed-loop (FCL) mode, with the exception of using their insulin-to-carbohydrate ratio as usual during 1 dinner in the house/hotel session of the study and 1 day at home and announcing eating initiation for 1 day at home. This study also includes a 1-week control period gathering data on glycemic control and insulin administration with the participants’ usual care therapy. Participants are randomized 1:1 to either Group A (control period prior to AIDANET use) or Group B (control period after AIDANET use).

Following Steps 1 and 2 described above, we developed a new version of the AIDANET bolus priming system (BPS) that uses reinforcement learning to determine pre-meal bolus amounts. Reinforcement learning (RL) is a branch of machine learning where an agent, like a neural network, learns to make decisions by interacting with its environment. Through trial and error, the agent receives feedback (rewards or penalties) for its actions, allowing it to refine its strategy over

time and maximize the total reward. By training our BPS using RL in an FDA-approved virtual environment, we developed a pre-meal bolus strategy optimized at the population level, meaning it works effectively for all patients. This updated BPS-RL is also able to analyze three days of glucose and insulin data to identify patterns and optimize the priming bolus, whereas the current BPS only uses the last 30 minutes of data. Moving forward, the RL-based system will allow for further personalization using patient-specific data in future research studies.

This protocol is the third step in the development of the next-generation AID algorithms that begin to use machine learning to adapt to the changing state of the person wearing the AID system. The goal of the protocol is to assess whether AIDANET plus reinforcement learning trained BPS (AIDANET+ BPS_RL) continues to provide safe and effective glycemia management as seen in prior studies.

(Note: Each of the previous referenced studies conducted at UVA were in compliance with 21 CFR parts 50, 56, and 812.)

Chapter 2: Study Synopsis

The new element of the AIDANET system to be tested in this study is the addition of a new BPS using machine learning to adapt and gradually improve the bolus-priming function of the system. It is anticipated that this is a step towards adaptive learning AID systems, potentially leading to completely FCL insulin delivery. All other elements of the AIDANET system described below, including the prototyping platform (the DiAs phone), the insulin pump, and the CGM sensor remain unchanged.

2.1 Study Objective

This study aims to demonstrate the safety and feasibility of the AIDANET+ BPS_RL algorithm, which replaces the BPS module in the previously tested AIDANET system with a new reinforcement learning trained BPS (BPS_RL).

2.2 Specific Aims and Hypotheses

Aim 1: To evaluate the performance (safety, efficacy) of AIDANET+ BPS_RL used as FCL.

Hypothesis: AIDANET+ BPS_RL use will result in equivalent or better Time in Range (TIR) than AIDANET (including current BPS) during two 18-hour hotel sessions (randomized crossover).

[figure not shown]
Aim 2: To evaluate the safety and efficacy of AIDANET+ BPS_RL at home.

Hypothesis: AIDANET+ BPS_RL use will result in equivalent or better TIR than AIDANET alone, during a week of At-Home use (repeated measures).

2.3 Study Design

This study is a randomized cross-over trial comparing AIDANET (including the current BPS) to AIDANET+ BPS_RL which includes the new BPS_RL (Figure 1). A week of AIDANET control at home will be followed by a two-night hotel session when participants will cross over from AIDANET to AIDANET+ BPS_RL and vice versa and will use new BPS_RL for a subsequent AIDANET+ BPS_RL week at home. For the majority of time, the participants will not announce meal ingestion to the system, thereby using the system in FCL mode of operation. However, the AIDANET system is designed to also work in hybrid closed-loop (HCL) mode with carbohydrate announcement, if requested by the user; thus, users will be allowed to enter carbohydrate amounts, which will be recorded by the system.

AIDANET+BPS_RL Study Timeline

Completion goal **N=16** subjects

Figure 1: Study Design

2.4 Study Hardware/Software

The study will involve using the previously tested AIDANET system, now equipped with a new BPS_RL designed to enable FCL and consisting of the following elements: the diabetes assistant (DiAs) prototyping platform, connected to a Tandem t:AP research insulin pump and a Dexcom G6 CGM.

2.5 Timing of Device Use

Following screening and randomization, all participants will be trained on the use of the study equipment and AIDANET algorithm. Participants will be connected to a Dexcom G6 sensor and the Tandem t:AP pump, which will be connected to the DiAs platform. AIDANET will be started on DiAs, and the participants will be trained how to use the Dexcom G6 sensor (if using Dexcom G7 in their AID system), the Tandem t:AP pump, and DiAs/AIDANET (see Table 1 and Figure 1). The t:AP pump will be programmed with back up parameters determined by the study investigator(s). Once started, the participants will have their glucose values managed through use of this system during the At-Home and hotel periods.

One-Week AIDANET: All participants will collect approximately one week of AIDANET baseline data. During this period, participants will generally use AIDANET in FCL mode. The DiAs Remote Monitoring will be on, supervised by study personnel.

Hotel Session: Participants will arrive at the hotel in the afternoon (prior to dinner). Those randomized to Group A will continue to use their AIDANET system. Those randomized to Group B will be switched to the AIDANET+BPS_RL system. Because AIDANET and AIDANET+BPS_RL have identical user interfaces and only the priming bolus calculation is changed “under the hood,” no additional training will be needed.

One-Week AIDANET+ BPS_RL: Participants will continue to use the Tandem t:AP pump, DiAs platform running the AIDANET+ BPS_RL, and Dexcom G6 CGM for glucose control for 7 days/6

243 nights during this period. The DiAs Remote Monitoring will be on, supervised by study personnel.
244 At the end of this period participants will return to their usual diabetes therapy.

245 **2.6 Meal Testing**

246 During the home study, participants will be instructed to consume their usual diet and will not be
247 required to record the timing of the meals. 2.3

248 **2.7 Study Devices Download**

249 Data from the study devices will be captured in real-time by the remote monitoring server for the
250 DiAs system. In addition, study devices will be downloaded at the end of the home visits.

251 **2.8 Study System Issues**

252 If the CGM signal becomes unavailable for more than 20 minutes consecutively, closed loop will
253 not operate to automatically adjust insulin delivery. If the CGM is not connected, the system will
254 revert to the usual open loop function of the pump and deliver insulin with the pre-programmed
255 dosing parameters. Resumption of closed-loop control will occur automatically once the CGM
256 signal is again available.

257 If the DiAs system is unable to maintain connectivity with the Tandem t:AP pump, the pump will
258 automatically revert to the pre-programmed dosing parameters after 30 minutes without any need
259 for interaction from the user.

Chapter 3: Study Screening

Visit 1

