4.1 Insulin Pump and DiAs

4.1.1 Equipment Description.

A study insulin pump and DiAs will be provided to all participants at this training visit.

The t:AP research insulin pump will be programmed with the participants' usual pump parameters (basal insulin rate, insulin to carbohydrate ratio, and insulin correction factor) as determined by the study physician. These parameters serve as backup-only settings for the system in open loop mode, and do not determine behavior of the AIDANET algorithm. The bolus priming system (BPS) profile determines the maximum fraction of total daily insulin (TDI) that can be injected by the BPS depending on the time of day (e.g., 8% between 06:00 and 10:00). The BPS profile is a setting on DiAs which can be modified by the provider to impact performance of the AIDANET algorithm. The study physician may alter the BPS profile during the hotel session and At-Home portions of the study to optimize participant safety with the experimental system.

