6.4 Study Meals

Participants will eat approximately 3 freely chosen unannounced meals per day during the supervised hotel session. Study staff will record the time the meal was eaten so that analysis of the AIDANET algorithm's performance around the mealtime may be conducted. Snacks with carbohydrates will not be allowed unless for the treatment of low blood sugars. Non-carbohydrate snacks may be allowed throughout the hotel session per investigator discretion. Blood glucose levels will be followed via CGM with interventions for glucose extremes as per the Glycemic Treatment Guidelines.

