12.1 Design and Randomization

This pilot study aims to demonstrate the safety and feasibility of the AIDANET+BPS_RL algorithm, which replaces with a new BPS_RL the bolus priming module of our AIDANET system described in IDE #G240236, which was approved by the FDA on October 10, 2024.

As presented in Figure 1, this study is a randomized cross-over trial comparing AIDANET to AIDANET+BPS_RL, which includes the new BPS_RL. A week of AIDANET control at home will be followed by a two-night hotel stay where participants will cross over from AIDANET to AIDANET+BPS_RL and vice versa and will learn how to operate the new BPS_RL for a subsequent AIDANET+BPS_RL week at home. The participants are not expected or encouraged to announce meals to the system, thus the system will run in fully-automated closed loop (FCL) mode.

Eligible participants will be randomized to two groups, A and B, which differ only by the order of administration of AIDANET or AIDANET+BPS_RL during the hotel section of the study. The remaining procedures are identical for both groups A and B. The randomization list will use a sequence of computer-generated pseudorandom Bernoulli trials and will aim to balance groups by baseline HbA1c (Figure 1).

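### No masking is described for the hotel crossover although the two algorithms look the same to the user; participants could be masked to the order at little cost

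*Combined protocol and SAP*

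**What the plan says.** Section 12.1 describes the design: "this study is a randomized cross-over trial comparing AIDANET to AIDANET+BPS_RL, which includes the new BPS_RL". Neither there nor in 2.3, 2.5, 3.11, Chapter 6 or the rest of Chapter 12 is there any statement on masking, open-label conduct or concealment of the order.

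On the two algorithms, 2.5 says: "Because AIDANET and AIDANET+BPS_RL have identical user interfaces and only the priming bolus calculation is changed". It concludes that no further training is required. The same section applies the allocation at hotel arrival. Group A carries on with the system it already has; for the other group, "Those randomized to Group B will be switched to the AIDANET+BPS_RL system". Randomization is scheduled at Visit 1 (Table 1, 3.11), and the hotel stay starts on Day 11. Section 12.1 adds that participants will learn during the hotel stay how to use the new module.

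On what participants and staff may do during the two sessions:
- 6.4: "Participants will eat approximately 3 freely chosen unannounced meals per day during the supervised hotel session".
- 4.1.1: "The study physician may alter the BPS profile during the hotel session and At-Home portions of the study".
- 6.6.2 leaves site changes and correction boluses to be considered when hyperglycemia is unexplained.
- 2.3: "thus, users will be allowed to enter carbohydrate amounts, which will be recorded by the system". Section 12.1 limits this: "The participants are not expected or encouraged to announce meals to the system".

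The primary outcome is CGM time in range from 6 PM to noon, covering one dinner and one breakfast (12.3). The TIR success criterion in 12.6 is a positive difference, whatever the p-value.

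**The concern.** Randomizing the order balances period effects. It does nothing about behavior that follows the algorithm itself. If participants eat differently, or staff act differently, because they know which version is running, that difference adds directly to the treatment contrast.

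The setting makes this plausible. Each window holds only two meals, the participant chooses them, and the module under test acts on meals. The bolus-priming profile caps the very bolus being compared, and it may be changed at discretion during the stay.

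Two results are exposed: the TIR success criterion, which depends only on the sign of the mean difference, and the effect size that the pilot is meant to hand on to the planned study of 50 completers (12.2, 12.6).

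**Working it through.** **1. Is masking feasible, and is awareness likely?** Two statements bear on this.
- 2.5: same interface, only an internal calculation differs, no retraining. A participant could use either version without being told which it is.
- 12.1: participants learn in the hotel how to use the new module. That presupposes they know when they have it.

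The two statements do not fit together. With the visible difference between carrying on (Group A) and being switched (Group B), the natural reading is that participants know the order.

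**2. Routes from awareness to TIR, by strength.**
- Freely chosen meals (6.4): the best-supported route. Meals are not matched between sessions.
- Profile changes (4.1.1), site changes and correction boluses (6.6.2): discretionary, with no stated concealment.
- Carbohydrate entry (2.3): weak in the hotel, because meals there are meant to be unannounced (6.4, 12.1).

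**3. The plan's own figure.** Sections 12.2 and 12.6 set f = 0.2, and 12.2 gives N = 50 for the later study. Alpha, power and within-person correlation are not stated. Assume two-sided alpha 0.05, power 0.80 and correlation rho = 0.5. For two conditions d = 2f = 0.4, and the standardized paired difference is d/√(2(1−rho)) = 0.4/√1 = 0.4. The normal approximation gives ((1.960 + 0.842)/0.4)² = 49.1, rounded up to 50. The noncentral t gives 52. So N = 50 is reproduced under these assumptions. Under them, pilot power is 0.30 (N = 15, section 12.2) or 0.32 (N = 16, protocol summary), in line with the stated figure of under 50%. Other correlations give other answers: N = 101, 71 and 32 at rho = 0, 0.3 and 0.7.

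**4. Effect of a bias on the sign criterion.** Let b be the bias in SDs of the paired difference. The documents give no value, so b is assumed. With no true effect, P(mean difference > 0) = Φ(b√N):

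| b | N = 15 | N = 16 |
|---|---|---|
| 0 | 0.50 | 0.50 |
| +0.1 | 0.65 | Φ(0.4) = 0.66 |
| +0.2 | 0.78 | Φ(0.8) = 0.79 |
| +0.4 | 0.94 | Φ(1.6) = 0.95 |

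Negative b gives the complements, for example 0.34 and 0.21 at b = −0.1 and −0.2 with N = 16. If the true effect is 0.4, the chance with N = 16 is Φ(1.6) = 0.95 without bias and Φ((0.4 − 0.2) × 4) = Φ(0.8) = 0.79 with b = −0.2.

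**5. Effect on the later study.** If an observed 0.4 included b = +0.1, the true value would be 0.3, and the formula in step 3 would give (2.802/0.3)² = 87.2, or 88 completers rather than 50.

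**6. Scale of one participant's change.** One hour in an 18-hour window is 1/18 = 5.6 TIR points for that participant. In the mean of 16 it is 5.6/16 = 0.35 points.

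**The case against.** The case against has real force.

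- **Silence is not a declaration.** A reader might infer that the trial is stated to be open label, or that participants are told their order. The text says neither. The consent pages and Figure 1 are not in the reviewed text. What stands is that no masking is described and that awareness is the natural reading.
- **Much is already standardized.** TIR is device-measured, the glucose triggers in 6.6 are the same for both algorithms, carbohydrate snacks are barred except to treat lows, and staff record meal times (6.4). These narrow the routes. They do not close them, because an objective sensor still registers a different meal or a changed setting.
- **The direction is unknown.** A reader might infer that expectation favors the new module. Trust in it could equally lead to larger meals and lower TIR. Only a possible bias, of either sign, is supported.
- **Size.** A reader might set the 5.6 points from one hour against the target effect. That compares one person's change with a group mean: all 16 would have to shift by an hour in the same direction to move the mean that far.
- **Masking may be imperfect.** Participants come straight from a week on AIDANET, and monitoring staff see insulin delivery in real time (6.2). Masking all staff is doubtful, and the physician who may alter the profile for safety may need to know. This limits staff masking but does not make participant masking pointless.
- **It is a pilot.** Power is under 50%, superiority is left to a later study, and the sign of the TIR difference is one success criterion among several. This limits the weight of the point. It does not remove it, since informing that later study is the pilot's stated use.

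**Conclusion.** The point holds as a cheap design improvement, not as a defect that invalidates the trial. The plan describes no masking in a comparison where its own text suggests participants could be masked, and it gives no reason. Knowledge of the algorithm could bias the hotel TIR contrast in either direction, chiefly through meals and discretionary profile changes and corrections.

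The size cannot be estimated from the documents. The calculations show sensitivity only: modest assumed biases of 0.1 to 0.2 SD move the null chance of meeting the TIR criterion from 0.50 to 0.66–0.79, or down to 0.34–0.21, with 16 completers. They rest on a normal approximation for the mean paired difference. Reading 0.4 SD as the target effect further requires a within-person correlation of 0.5, which the plan does not state. Feasibility rests on the claim in 2.5 that the interfaces are identical, taken to include anything on screen that names the version.

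**What to change.** 1. Mask participants to the algorithm order during both hotel sessions, until noon on Day 3. A designated unmasked team member, for example the engineer already on call under 6.2, loads the algorithm by participant code.
2. Perform the same apparent switch for every participant at both session starts, so that carrying on versus being switched does not reveal the order. Check that no version name shows on the phone.
3. Where feasible, do not tell the staff who record meals. Monitoring staff and the study physician may stay unmasked for safety. Record any unmasking, with time and reason.
4. Reconcile the statement in 2.5 that no further training is required with the statement in 12.1 that participants learn the new module in the hotel.
5. Report meals, carbohydrate entries, bolus-priming profile changes and interventions by algorithm for the two 18-hour windows.
6. If the sponsor prefers an open design, say so and justify it; item 5 is then the minimum.

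The cost is a short coding and unmasking procedure, plus someone available to load the algorithm at each session start. The engineer is described only as on call, so attendance may need arranging. The home weeks are unaffected, since everyone uses the same algorithm in each.
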